3. PATIENT SELECTION

3.1 Inclusion Criteria

- 3.1.1 Female greater than or equal to 18 years.
- 3.1.2 Eastern Cooperative Oncology Group (ECOG) performance status ≤ 2 (see Appendix A).
- 3.1.3 Histologically confirmed adenocarcinoma of the breast.
- 3.1.4 Evidence of hormone insensitivity (ER and PR negative) of primary tumor tissue. ER negative is defined as ER 0 or $< 1\%$ staining by immunohistochemistry. PR negativity is defined as PR $\leq 10\%$ staining by immunohistochemistry.
- 3.1.5 HER2 negative in the primary tumor tissue as defined by:
 - Immunohistochemistry (IHC) Grade 0 as defined by no staining observed or membrane staining that is incomplete and is faint/barely perceptible and within $\leq 10\%$ of the invasive tumor cell
 - IHC 1+ as defined by incomplete membrane staining that is faint/barely perceptible and within $> 10\%$ of the invasive tumor cell
 - IHC Grade 2+ staining intensity by means of IHC analysis with no gene amplification below.
 - No gene amplification on ISH based on
 - Single-probe average HER2 copy number < 4.0 signals/cell
 - Dual-probe HER2/CEP17 ratio < 2.0 with an average HER2 copy number < 4.0 signals/cell
- 3.1.6 Ability to understand and the willingness to sign a written informed consent document.
- 3.1.7 Patients must not have received any prior chemotherapy, radiation therapy, or endocrine therapy for their current breast cancer. Patients who received tamoxifen or raloxifene or another agent for prevention of breast cancer may be included as long as the patient has discontinued the treatment at least one month prior to baseline study biopsy.
- 3.1.8 Women of childbearing potential must have negative (serum or urine) pregnancy test within 7 days prior to registration.
- 3.1.9 Patients must have adequate tumor tissue sample prior to the enrolment available for correlative studies as defined below:
 - Core needle biopsy or incisional biopsy samples that can provide ≥ 3 unstained sections of 5 micron thickness. Fine needle aspiration (FNA) sample alone is not sufficient except in the second cohort.
 - Additional core needle biopsy needs to be performed in the patients who agree to participate in this study and do not have adequate tumor tissue sample.
 - 3.1.10 Patients must have adequate organ and marrow function as defined below:
 - Hemoglobin ≥ 9.0 g/dL
 - Leukocytes $\geq 2,500$ /mcL
 - Absolute neutrophil count $\geq 1,100$ /mcL
 - Platelets $\geq 100,000$ /mcL
 - Total bilirubin within normal institutional limits
 - AST(SGOT)/ALT(SGPT) ≤ 2.5 x institutional upper limit of normal
 - Creatinine within normal institutional limits or creatinine clearance ≥ 60 mL/min/1.73 m² for patients with creatinine levels above institutional normal

Additional Inclusion Criteria for the First cohort:

- 3.1.11 Unresected operable breast cancer that meets the following clinical stages (see Appendix B):
 - T1b, T1c, or T2
 - N0 or N1
 - M0 (No distant metastasis)

Additional Inclusion Criteria for the Second cohort:

- 3.1.12 Unresectable, inoperable, recurrent local-regional breast cancer or
- 3.1.13 Metastatic (stage IV) breast cancer
- 3.1.14 Patients must have measurable or evaluable disease (i.e. ascites or pleural/pericardial effusion). Patients with bone metastatic only will be excluded.
- 3.1.15 Patients must not have rapidly progressive disease, extensive visceral involvement, or any high risk characteristics that are not appropriate for this treatment as per investigator's discretion.
- 3.1.16 Patients must receive at least one prior line of chemotherapy but not more 2 prior chemotherapy regimens for stage IV breast cancer. Prior chemotherapy in the adjuvant and /or neoadjuvant setting is permitted. However, patients must have finished chemotherapy at least 2 weeks prior to enrollment.
- 3.1.17 Patients must have an accessible tumor lesion from which a fine needle aspirate or preferably a core biopsy specimen can be obtained. Patients with FNA only samples are allowed in this cohort. Ascites or pleural/pericardial effusion alone is not sufficient.

- 3.1.18 Patients must be willing to provide consents for 2 research biopsies. However, the pretreatment biopsy can be omitted in patients who have recent biopsy but have not been started on breast cancer treatment within 12 weeks prior to the registration and there is adequate tumor tissue sample as per section 3.1.9.

3.2 Exclusion Criteria

- 3.2.1 Patients may not be receiving any other investigational agents.
- 3.2.2 Prior exposure to other HDAC inhibitors. However, prior valproic acid exposure is allowed providing ≥ 30 days wash-out period.
- 3.2.3 History of allergic reactions or hypersensitivity to compounds of similar chemical or biologic composition to entinostat, benzamide, anastrozole, or tamoxifen.
- 3.2.4 Any medical condition which in the opinion of the investigator puts the patient at risk of potentially serious complications while on this therapy.
Examples: HIV, unstable angina, uncontrolled heart failure or hypertension, uncontrolled hyperlipidemia, uncontrolled diabetes mellitus, uncontrolled systemic infection.
- 3.2.5 Previous or current systemic malignancy within the past 3 years other than breast cancer or adequately treated cervical carcinoma in situ or basal/squamous carcinoma of the skin.

3.3 Inclusion of Minorities

Women of all races and ethnic groups are eligible for this trial.

Accrual Targets			
Ethnic Category	Sex/Gender		
	Females	Males	Total
Hispanic or Latino	10	+ 0	= 10
Not Hispanic or Latino	35	+ 0	= 35
Ethnic Category: Total of all subjects	45 (A1)	+ 0 (B1)	= 45 (C1)
Racial Category			
American Indian or Alaskan Native	5	+ 0	= 5
Asian	5	+ 0	= 5
Black or African American	5	+ 0	= 5
Native Hawaiian or other Pacific Islander	5	+ 0	= 5
White	25	+ 0	= 25
Racial Category: Total of all subjects	45 (A2)	+ 0 (B2)	= 45 (C2)

Accrual Rate: 2-3 pts/month Total Expected Accrual: 12 Min 45 Max

4. REGISTRATION PROCEDURES

4.1 General Guidelines

Eligible patients will be entered on study at the University of Maryland Greenebaum Cancer Center by the Study Coordinator. Following registration, patients should begin protocol treatment within 3 business days. All of the patients' documents must be kept confidential in a secured area.

To register a patient, the following documents should be completed by a research team member and sent to the Study Coordinator, [name] or [name], via fax, [contact], or e-mail, [contact] or [contact]

- Copy of required laboratory tests
- Signed patient consent form
- HIPAA authorization form
- Other appropriate forms (e.g., Eligibility Screening Worksheet, Documentation of Pathology and Diagnosis, Registration Form)

To complete the registration process, the Coordinator will

- Assign the patient a study number
- Register the patient on the study

4.2 Pretrial Screening

Patients will be screened at the participating centers before entry to establish eligibility. The following assessments must be obtained within 3 weeks of trial entry:

- Medical history including all significant conditions.
- Concomitant therapy before entry documented to establish eligibility.
- ECOG performance status
- Physical examination including vital signs, height and weight
- Clinical tumor assessment by a breast examination including clinical tumor size, character, mobility, and location of the breast mass.
- Laboratory studies: CBC with diff; chemistries including sodium, potassium, chloride, bicarbonate, BUN, creatinine, glucose, total bilirubin, calcium, total protein, albumin, AST (SGOT), ALT (SGPT), alkaline phosphatase, LDH, uric acid, phosphorus, magnesium; and coagulation including PT with INR and PTT
- 12-lead electrocardiogram (ECG) at baseline

Following baseline breast imaging can be obtained within 6 weeks of trial entry:

- Baseline mammogram, breast ultrasound, or breast magnetic resonance imaging (MRI) as indicated

5. TREATMENT PLAN

5.1 Agent Administration

Treatment will be administered on an outpatient basis. Reported adverse events and potential risks for anastrozole and entinostat are described in Section 7. Appropriate dose modifications for entinostat and anastrozole are described in Section 6. No investigational or commercial agents or therapies other than entinostat, anastrozole, and tamoxifen may be administered with the intent to treat the patient's malignancy.

In the first cohort:

- Treatment will be continued for a minimum of 15 days and a maximum of 29 days. If clinically acceptable, treatment should be preferably continued for 22 days prior to the definitive surgery.
- Anastrozole will be administered continuously starting on day 4 at a fixed dose of 1 mg oral once daily.
- In patients who are not postmenopause as defined by any of the following criteria, tamoxifen will be administered continuously instead of anastrozole starting on day 4 at a fixed dose of 20 mg oral once daily.

Postmenopausal as defined by any of the following criteria:

- Age \geq 60
- Age < 60 with amenorrhea > 12 months and an intact uterus and an FSH and estradiol level within the postmenopausal range by institutional laboratory parameters.
- Age < 60 with previous hysterectomy must have FSH and estradiol level within the postmenopausal range by institutional laboratory parameters.
- Any age having undergone bilateral oophorectomy
- Entinostat will be administered at the assigned dose once a week (on day 1, 8, 15, 22, and 29) until the definitive surgery. Entinostat should be taken with a meal after the first two or three bites.
 - The initial starting dose for entinostat is 5 mg oral weekly. Dose de-escalation to 3 mg/week is permitted in the pilot phase if dose limiting toxicity is observed as defined in section 5.2.1.
 - Dose level for entinostat in phase II part of this study will be determined after the pilot phase is completed.

In the second cohort:

1. Pretreatment biopsy (biopsy#1) will be performed within 3 weeks after registration. However, the pretreatment biopsy can be omitted in patients who have recent biopsy but have not been started on breast cancer treatment within 12 weeks prior to the registration and there is adequate tumor tissue sample as per section 3.1.9.
- Treatment will be started after pretreatment biopsy and will be continued until disease progression. The post-treatment biopsy (biopsy#2) will be performed after a minimum of 15 days and a maximum of 29 days of treatment, but preferably close to 29 days. The post-treatment biopsy must take place within 6 days (preferably within 3 days) after the last dose of entinostat. After the post-treatment biopsy, treatment will be continued until disease progression regardless of the result of post-treatment biopsy. Restaging scans will be performed every 6 weeks while on treatment. In the event that a patient cannot undergo the post-treatment biopsy for any reason, they will continue to be treated per study protocol. If a patient discontinues the study prior to 15 days, an attempt should be made to collect the biopsy when the decision is made to discontinue and prior to initiation of additional treatment, if possible.
 - Anastrozole will be administered continuously starting on day 4 at a fixed dose of 1 mg oral once daily until disease progression.
 - In patients who are not postmenopause as defined by any of the previously described criteria, tamoxifen will be administered continuously instead of anastrozole starting on day 4 at a fixed dose of 20 mg oral once daily until disease progression.
 - Entinostat will be administered at the assigned dose once a week until disease progression. Entinostat should be taken with a meal after the first two or three bites.
 - The initial starting dose for entinostat is 5 mg oral weekly. Dose de-escalation to 3 mg/week is permitted if dose limiting toxicity is observed as defined in section 5.2.1.
 - Dose level for entinostat in phase II part of this study will be determined after the pilot phase is completed.

The dose schemas are as shown below for both postmenopausal and premenopausal women:

Dose Modification Schema for Postmenopausal Women		
Dose Level	Dose	
	Entinostat (mg)	Anastrozole (mg) daily
-1	3 mg weekly (on day 1, 8, 15, 22, and 29)	1
1	5 mg weekly (on day 1, 8, 15, 22, and 29)	1

or

Dose Modification Schema for Premenopausal Women		
Dose Level	Dose	
	Entinostat (mg)	Tamoxifen (mg) daily
-1	3 mg weekly (on day 1, 8, 15, 22, and 29)	20
1	5 mg weekly (on day 1, 8, 15, 22, and 29)	20

5.1.1 Entinostat

Entinostat is supplied as light brown (1 mg) or intense yellow (5 mg) coated tablets. Patients will self-administer entinostat as per assigned dose level shown in section 6.1. Tablets should be taken with a meal after the first two or three bites. If the patient's dose requires more than one tablet, the tablets should be taken one at a time. Unused tablets or empty bottles will be returned to the clinic for accountability purposes. Dose reductions for toxicity are summarized in section 6.2. The definitive surgery or post-treatment biopsy (biopsy#2) must take place within 6 days (preferably within 3 days) after the last dose of entinostat.

Entinostat may cause fatigue or malaise; advise patient to exercise caution while driving a vehicle or operating machinery. Delay administration of H₂-antagonists, antacids, or proton pump inhibitors, or other drugs that lower acidity for at least 2 hours after dosing entinostat.

5.1.2 Anastrozole

Anastrozole will be taken by mouth once daily on a continuous basis starting on day 4 at the fixed dose of 1 mg per day. Anastrozole should be continued until the day of the surgery in the first cohort and until disease progression in the second cohort.

5.1.3 Tamoxifen

In patients who are not postmenopause as defined in section 5.1 (premenopausal women), tamoxifen will be administered instead of anastrozole. Tamoxifen will be taken by mouth once daily on a continuous basis starting on day 4 at the fixed dose of 20 mg per day. Tamoxifen should be continued until the day of the surgery in the first cohort and until disease progression in the second cohort.

Dose Modification Schema for Premenopausal Women		
Dose Level	Dose	
	Entinostat (mg)	Tamoxifen (mg) daily
-1	3 mg weekly (on day 1, 8, 15, 22, and 29)	20
1	5 mg weekly (on day 1, 8, 15, 22, and 29)	20

Therefore, the total number of patients for the pilot phase of the study will be 6-12 for each treatment groups (entinostat and anastrozole as well as entinostat and tamoxifen) or the total of 12-24 patients.

The phase II part will continue with the dose level in which there is ≤ 1 out of 6 patients experiencing a DLT. However, if there are ≥ 2 out of 6 patients experiencing DLT at dose level -1, the study will be terminated due to toxicity.

The patients in the pilot phase will be included in the overall evaluation of response.

Toxicity will be graded according to the active version of National Cancer Institute (NCI)-Common Terminology Criteria for Adverse Events (CTCAE) as per section 7.3. Patients in both cohorts (the first cohort-operable stage I-II and the second cohort-unresectable locally advance/metastatic) in the pilot phase will be used to evaluate for DLT. In the second cohort, only adverse events (AEs) that occur during the first 29 day will be considered for DLT. DLT is defined as one or more of the following treatment-related:

1. Hematologic AEs
 - a. Absolute neutrophil count (ANC) $< 500/\text{mm}^3$ regardless of duration
 - b. Failure of ANC to recover $\geq 1,000/\text{mm}^3$ within 14 days
 - c. Grade ≥ 4 thrombocytopenia regardless of duration or grade 3 thrombocytopenia with significant bleeding.
 - d. Failure of platelet to recover $\geq 50,000/\text{mm}^3$ within 14 days
 - e. Hemoglobin < 6.5 g/dL despite transfusion lasting > 7 days
2. Grade ≥ 3 nonhematologic AEs (except for fatigue, diarrhea, and nausea/vomiting if manageable).
3. Grade ≥ 3 diarrhea lasting > 2 days despite being treated with optimal medical therapy, or associated with fever or severe dehydration.
4. Grade ≥ 3 fatigue lasting > 7 consecutive days.

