12. STATISTICAL CONSIDERATIONS

12.1 Study Design/Endpoints

This is a Pilot and Phase II, single-arm, open-labeled, multi-center study of entinostat in combination with anastrozole/tamoxifen in women with triple negative breast cancer. The main objective of this study is to assess the safety and efficacy of the combination of entinostat and anastrozole/tamoxifen. The primary endpoints, that we will use to evaluate the efficacy of the entinostat and anastrozole/tamoxifen, are the reduction in proliferative index (Ki67) and upregulation of ER after treatment with entinostat and anastrozole/tamoxifen therapy. We define patient's response as at least 50% reduction in the Ki67 index AND greater than 1% ER-positivity OR pathologic complete response in the post-treatment surgical specimens. For the evaluation of these biological endpoints, the analysis will include ALL of the patients in both cohorts (the first cohort-operable stage I-II and the second cohort-unresectable locally advanced/metastatic) as well as both anastrozole and tamoxifen groups.

In the pilot phase, the classic cohort-of-3-study design will be used. The primary endpoint of this part of the study is to determine the recommended dose for the phase II part as well as to evaluate the safety of both combinations. The dose levels are defined below for both pre- and postmenopausal groups. For safety, each combination (entinostat and anastrozole as well as entinostat and tamoxifen) will be evaluated separately. For both groups (anastrozole and tamoxifen), the first cohort of 3 patients will be treated starting at dose level 1 (d_1). If ≤ 1 patient experiences DLT, an additional 3 patients will be treated at this dose level (d_1). If ≥ 2 patients in the initial cohort of 6 patients suffer DLT, then up to 6 additional patients will be enrolled at the dose level -1. The phase II part will continue with the highest dose level with < 2 out of 6 patients experiencing a DLT. Therefore, we will need 6-12 patients for each combination

in this part of the study. The 6 patients from the pilot phase of each combination that are treated with the recommended dose level for the phase II will be included in the primary endpoint analysis.

The dose modification schemas are as follow for both postmenopausal and premenopausal women:

Dose Modification Schema for Postmenopausal Women		
Dose Level	Dose	
	Entinostat (mg)	Anastrozole (mg) daily
-1	3 mg weekly (on day 1, 8, 15, 22, and 29)	1

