1	5 mg weekly (on day 1, 8, 15, 22, and 29)	1

or

Dose Modification Schema for Premenopausal Women		
Dose Level	Dose	
	Entinostat (mg)	Tamoxifen (mg) daily
-1	3 mg weekly (on day 1, 8, 15, 22, and 29)	20
1	5 mg weekly (on day 1, 8, 15, 22, and 29)	20

In the phase II part, the Simon's two-stage design will be used for the study to ensure that the number of patients exposed to this new treatment is minimized. The analysis for this part of the study will include ALL of the patients in both cohorts (the first cohort-operable stage I-II and the second cohort-unresectable locally advance/metastatic) as well as both anastrozole and tamoxifen groups. The total sample size for the phase II part of the study is 32 with 12 and 20 patients in the first and second stage respectively. The 6 patients in the pilot phase of each combination that are treated with the recommended dose level for phase II will be included in the first stage of the phase II part of the study. The study will be terminated, if there is no response among the first 12 patients. If ≥ 1 response in these 12 patients is observed, then 20 more patients will be accrued. The combination will be considered promising, if ≥ 4 out of 32 patients have a response. This design yields 87% power. The probability of early stopping and declaring that this combination has no sufficient activity is 0.54, if the true success rate is 5% and 0.07 if the true response rate is 20%. If the true proportion of patients with Ki67 reduction combined with ER up-regulation is 0.20, the probability of concluding that the drug has sufficient activity is 0.87 and 0.07 if the true proportion is 0.05. To allow about 10% inevaluability, the phase II trial will accrue 35 eligible patients. Statistical analysis will be done using S-plus (TIBCO, version 8.0). All descriptive statistics will be reported. The multivariate analysis of variance or its non-parametric alternative will be applied to compare biomarkers' expression levels. The 90% confidence intervals will be constructed for the observed proportions. All statistical tests will be two-sided, and done at the 0.05 level of significance.

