12.2 Sample Size/Accrual Rate

For the pilot phase, the study will require 12-24 patients to complete, allowing for 3-6 patients per dose level and 2 predefined dose levels for 2 combination treatments (entinostat and anastrozole as well as entinostat and tamoxifen). In the phase II period, the study will require 12-35 patients to complete. However, we will include the 12 patients in the pilot phase that are treated with the recommended dose level of each combination for phase II in the primary endpoint analysis. Therefore, the total sample size for this study is 12-41 patients. At an anticipated accrual rate of 15-20 patients/year, we anticipate that the phase II part will need to accrue patients for anywhere from 7 to 33 months.

NOTE: The maximum total sample size will most likely remain 41 patients. The only situation that this trial will require additional 6 patients is that there are ≥ 2 patients in the first cohort of 6 patients suffer DLT in dose level 1 in both combination treatments. As of November 2011, there were 3 patients enrolled in the pilot phase of this study. There is no DLT observed in this first 3 patients treated with entinostat and anastrozole. Furthermore, a phase II study of

entinostat and AIs including anastrozole was recently completed which demonstrated that this combination is safe and tolerable with the majority of AEs being only grade 1 or 2⁴⁷. Taken this together, it is highly unlikely that there will be ≥ 2 patients in the first cohort of 6 patients suffer DLT in dose level 1 in entinostat and anastrozole group.

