12.3 Analysis of Primary Endpoints

Pilot Phase

To address the safety of both regimens, a maximum width 90% confidence interval for any grade 3 or higher toxicity will be approximately 30%. For 35 patients in this study, if the true unknown probability of a rare toxicity is 10%, the probability of observing 1 or more toxicities is 97%, and if the true toxicity rate is 5% then the probability of observing one or more rare toxicities is 83%.

In the first cohort, because the study participants are awaiting a curative surgery, greater than 10% delay in surgery (more than 2 weeks) is unacceptable. Thus, if ≥ 2 delays are observed in the first ten participants, the dose will be de-escalated to level -1. If ≥ 2 additional delays are observed after dose modification, consideration will be made to further change in dose or schedule of study medication.

Phase II

Regarding the ER and Ki67 analysis, we will also include the evaluable patients from the pilot phase for this analysis. For the evaluation of these biological endpoints, the analysis will include ALL of the patients in both cohorts (the first cohort-operable stage I-II and the second cohort-unresectable locally advance/metastatic) as well as both anastrozole and tamoxifen groups. When the sample size is 41, a single-group repeated measures analysis of variance with a 0.05 significance level will have adequate above 80% power to detect a difference in average expression levels of ER and Ki67 between the baseline and after treatment values when an effect size is 0.1. With effect size of 0.125 and higher, power increases to 90%.

The 95% confidence intervals will be constructed for the observed proportions. Exploratory data analysis and appropriate graphs will be used to decide whether data transformation (e.g. log or square-root) is necessary to assure an approximate normality. All descriptive statistics will be reported for ER and Ki67 expression. We will use general linear model approach and/or its non parametric alternative, the Wilcoxon test, to assess whether there is any evidence of changes due to treatment. All statistical tests will be two-sided done at the 0.05 level of significance. Statistical analysis will be done using S-plus (TIBCO version 8.0).

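### Section 12.3 states Ki67/ER power at n = 41, a size that the primary set in 12.1 and 12.2 (32 evaluable, 35 accrued) cannot reach, and neither 12.3 nor 5.2.1 limits pilot patients by dose

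*Combined protocol and SAP*

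**What the plan says.** **Restricted to the recommended dose.**
- Section 12.1 limits the pilot contribution to six patients per combination, those "treated with the recommended dose level for the phase II will be included in the primary endpoint analysis". It puts the same patients into stage 1: they are "treated with the recommended dose level for phase II will be included in the first stage of the phase II part" of the study.
- Section 12.2 repeats this: "we will include the 12 patients in the pilot phase that are treated with the recommended dose level of each combination for phase II".
- The phase II size in 12.1 "is 32 with 12 and 20 patients in the first and second stage respectively". The trial stops if none of the first 12 responds and is promising if at least 4 of 32 respond. Accrual is raised to 35 to allow for about 10% inevaluable.

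**Not restricted by dose.**
- Section 5.2.1: "The patients in the pilot phase will be included in the overall evaluation of response". The same section puts the pilot size at "6-12 for each treatment groups (entinostat and anastrozole as well as entinostat and tamoxifen) or the total of 12-24 patients".
- Section 12.3, under the phase II primary analysis, brings in evaluable pilot patients with no mention of dose. It begins its power statement: "When the sample size is 41, a single-group repeated measures analysis of variance". It claims more than 80% power at an effect size of 0.1 and 90% at 0.125 and above.

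Section 12.1 defines a patient's response as the Ki67/ER composite or pathologic complete response. That is the outcome that the two-stage rule counts.

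**The concern.** If neither combination is de-escalated, every pilot patient is at the recommended dose and the passages agree on who is analysed. If one is de-escalated, they part: 12.1 and 12.2 leave out the patients treated at the dose not carried forward, while 5.2.1 and 12.3 can be read to include them. The analyst would then choose between the sets with the data in hand.

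The n in 12.3 is a problem whichever way the pilot goes. Without de-escalation the trial accrues at most 35, so 41 is never reached. With one de-escalation 41 is reached only by counting patients that 12.1 excludes. At stake are the population to which the Ki67/ER result applies and whether the stated power is available in it.

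**Working it through.** **1. Where 41 comes from.** Phase II accrual is 35 (12.1), and this already contains the 12 recommended-dose pilot patients (12.2). 41 − 35 = 6, which is one combination's six patients at the dose not carried forward. Section 12.2 says that six more would be needed only if both combinations are de-escalated: 35 + 12 = 47. These are accrual totals. On the evaluable scale they are 32 + 6 = 38 and 32 + 12 = 44 if every added patient is evaluable.

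**2. The two-stage rule as written.** Inputs from 12.1: n1 = 12, n = 32, stop at 0 of 12, success at 4 or more.

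P(promising) = Σ over x ≥ 1 of P(X1 = x) × P(X2 ≥ 4 − x), with X1 ~ Bin(12, p) and X2 ~ Bin(20, p).

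At p = 0.05:
- Early stopping: 0.95^12 = 0.540.
- P(X1 = 1, 2, 3, ≥4) = 0.3413, 0.0988, 0.0173, 0.0022.
- P(X2 ≥ 3, 2, 1) = 0.0755, 0.2642, 0.6415.
- Sum: 0.3413 × 0.0755 + 0.0988 × 0.2642 + 0.0173 × 0.6415 + 0.0022 = 0.065.

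At p = 0.20, early stopping is 0.80^12 = 0.069 and P(promising) is 0.866. All four stated figures (0.54, 0.07, 0.07, 0.87) reproduce.

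**3. The same rule if 5.2.1 were applied to it.** Add k patients treated at the dose not carried forward, keep the cut-off at 4, and let every patient's true rate be 5%.

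| k | Evaluable n | Type I error, first look at 12 | Type I error, first look at 12 + k |
|---|---|---|---|
| 0 | 32 | 0.065 | 0.065 |
| 6 | 38 | 0.099 | 0.114 |
| 12 | 44 | 0.137 | 0.172 |

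If these patients join the first look, early stopping at 5% falls from 0.540 to 0.95^18 = 0.397 or 0.95^24 = 0.292.

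**4. The 12.3 power.** Section 12.3 does not define its effect size. I took a noncentral F with 1 and n − 1 degrees of freedom, two-sided 0.05, and λ = c × n × effect size. With c = 2 the result at 41 is close to the stated 80% and 90%; with c = 1 or c = 4 it is not (0.506 and 0.977 at effect size 0.1). Results with c = 2:

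| n | λ at 0.1 | Power at 0.1 | λ at 0.125 | Power at 0.125 |
|---|---|---|---|---|
| 41 | 8.2 | 0.798 | 10.25 | 0.878 |
| 38 | 7.6 | 0.766 | 9.5 | 0.851 |
| 35 | 7.0 | 0.729 | 8.75 | 0.820 |
| 32 | 6.4 | 0.688 | 8.0 | 0.782 |

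For the range: at n = 32 and effect size 0.1, c = 1 gives 0.411 and c = 4 gives 0.934.

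**The case against.** A reader might infer that patients treated at a rejected dose enter the two-stage decision and inflate its type I error. The documents do not support that. Section 12.1 writes the rule as 4 of 32, names the recommended-dose pilot patients as part of stage 1, and reproduces exactly. No section applies a cut-off of 4 to 38, 41, 44 or 47 patients. The 41 belongs to a different analysis, a two-sided 0.05 test of mean change, whose type I error does not rise with n. This objection stands in full, and step 3 is only a conditional calculation.

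The sentence in 5.2.1 may also concern secondary response. Section 5.8 uses the same expression for keeping withdrawn patients in an intent-to-treat analysis. Section 12.4 estimates clinical and pathological response in all eligible patients and relates response to dose level, which needs patients at other doses. This stands in part: 5.2.1 can be read that way, but it does not say so, and 12.1 gives the word response a primary meaning.

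Finally, the mixed-dose problem needs a de-escalation. Section 12.2 reports no DLT in the first three anastrozole patients and calls two or more DLTs among the first six on that combination highly unlikely. That makes the problem less probable. It does not rescue the 41, and the reassurance does not extend to tamoxifen, for which 5.2.1 reports no earlier study with entinostat.

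**Conclusion.** The analysis set is inconsistent between 12.1/12.2 and 12.3, and 5.2.1 leaves it open. The 12.3 power is stated at an n that the primary set cannot reach.

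- **Size in 12.3.** At 32 evaluable patients, power is about 0.69 at effect size 0.1 and 0.78 at 0.125, against the stated 80% and 90%. This rests on λ = 2 × n × effect size, an assumption chosen because it comes close to the plan's own figures. If a combination is de-escalated, the test also mixes doses.
- **Two-stage rule.** Its stated error rates hold. Type I error would rise to about 0.10–0.11 (six added patients) or 0.14–0.17 (twelve) only if 5.2.1 were carried into the rule with the cut-off left at 4. The lower end of each range keeps the first look at 12 and the upper end adds these patients to it.

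This should be corrected before analysis, but it does not invalidate the decision rule.

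**What to change.** 1. In 5.2.1 and 12.3, state that the primary Ki67/ER analyses and the 4-of-32 rule use only pilot patients treated at the recommended dose of their combination, plus the phase II accrual.
2. In 12.3, define the effect size and restate the power at 32 evaluable patients. Under the assumption above, 80% power would need an effect slightly larger than 0.125.
3. Keep the remaining pilot patients for the secondary response and dose-level analyses in 12.4, and list them by dose. If a 41-patient analysis is wanted, label it supportive and all-treated.

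This takes wording in two sections and one recalculated power statement, with no added patients or procedures. The real cost is a less favourable power figure in 12.3, below 80% at effect size 0.1 under the assumption used here.
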